1.4. Pharmacokinetics (PK) and Pharmacodynamics (PD) Profile

Pharmacokinetics:

The absorption of inhaled epinephrine is rapid. In a multiple-dose systemic absorption of inhaled epinephrine study which enrolled six normal healthy volunteers, a rapid rise of plasma epinephrine levels with short duration were observed after administration of 15 puffs

followed by 30 puffs, with a >5 minute interval, at 160 mcg per puff. One minute after the initial 15 inhalations (2.4 mg) of epinephrine, the mean base-line epinephrine levels rose from 0.23 (± 0.02) to a peak of 1.50(± 0.61) nmol/L (i.e., 275 pg/ml). One minute after the subsequent 30 inhalations (a dose of 4.8 mg epinephrine), the epinephrine level rose to a peak of 4.22 (1.93) nmol/L (i.e., 772 pg/ml). The plasma epinephrine fell to baseline at 20 min after 30 inhalations of epinephrine ^[2].

Overall systemic sympathomimetic effects are minimized due to a very low systemic exposure (~5% bioavailability) after oral inhalation ^[3].

The systemic levels of albuterol are low after inhalation of recommended doses. The terminal plasma half-life of albuterol delivered by PROAIR HFA was approximately 6 hours.

Information from published literature suggests that the primary enzyme responsible for the metabolism of albuterol in humans is SULT1A3 (sulfotransferase). The primary route of elimination of albuterol is through renal excretion (80% to 100%) of either the parent compound or the primary metabolite. Less than 20% of the drug is detected in the feces.

Pharmacodynamics:

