3. STUDY DESIGN AND OUTCOMES

3.1 STUDY DESIGN

This study is a randomized, safety, evaluator-blinded, single dose, three-treatment, crossover, fasting study in healthy adult volunteers. The treatments and doses evaluated in this study are summarized in Table 1.

Table 1. Treatments and Dose

Items	Treatment-A	Treatment-B	Treatment-C
Study Drug Name	Primatene Mist, E004	Epinephrine Injection Auto-Injector (Generic of EpiPen®)	ProAir
Manufacturer			
API	Epinephrine	Epinephrine	Albuterol Sulfate
Dosage Form	Microcrystalline Suspension HFA MDI	Sterile Solution	Microcrystalline Suspension HFA MDI
Strength	0.125 mg/inh	0.3mg/0.3mL	0.09 mg/inh
Dose Regimen	2 inhalations, 0.25mg	IM Injection of 0.30 mg Epinephrine in 0.30 mL	2 inhalations, 0.180 mg
Route of Administration	Oral Inhalation	IM Injection	Oral Inhalation

The study is conducted in healthy male and female adult subjects at 18 to 50 years of age with a targeted total of 24 evaluable subjects at the completion of study.

The design includes one screening visit, three (3) study visits and a follow-up phone evaluation. All subjects will be screened for enrollment before being randomly assigned to one of the six treatment sequences by 3 x 3 Latin Square method.

According to the randomized treatment sequence, each qualified subject will be treated with one of the three (3) treatments at each study visit. At each study visit, 26 PK blood samples will be collected and plasma will be isolated for analyzing concentrations of albuterol and epinephrine. The three (3) study visits, and main study procedures, are outlined in Summary of Activities below (Table 2):

The three study visits, and main study procedures, are outlined in Study Schema:

Table 2. Summary of Activities in All Visits and EOS

Study Activities & Evaluations	Screen Visit	Dosing Visit-1	Dosing Visit-2 and 3	EOS ¹
Informed Consent / HIPAA	X			
Medical history / demographics	X			
Physical Exam (PE)	X			X
Lab: Urinalysis (UA)	X			X
Lab: CBC/Comp. metab. Panel	X			X
Lab: Thyroid Function	X			
Lab: HIV-Ab, HB-sAg, HCV-Ab	X			
Inclusion/Exclusion	X	X		
Confirmation of enrollment		X		
Assign subject ID		X		
Randomization		X		
Training/Dosing of MDI	X	X	X	
Concomitant Medicines		Record throughout study period		
Urine or serum pregnancy test	X	X	X	
Urine drug screen	X	X	X	
Alcohol screen (urine or breathalyzer)	X	X	X	
Food / beverage restrictions		X	X	
Meals served		X	X	
PK Baseline samples		X (1)	X (1)	
PK samples		X (25)	X (25)	

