4. CALCULATION OF RELATED STATISTICAL QUANTITIES

4.1 PK/PD PARAMETERS

4.1.1 Primary Endpoints

(1) C_{max} , in units of pg/mL, is defined as the maximum of experimental data points of epinephrine or albuterol concentration for a given subject and given treatment:

[figure not shown]
$$C_{max} = \max (C_1 \cdots C_i \cdots C_n) \quad i = 1, 2, 3 \cdots n \quad (1)$$

where C_i is the observed plasma concentration of albuterol or epinephrine at the time t_i ; which is the sampling point time;
 t_1 is the baseline, and n is the number of available PK measurements.

(2) $AUC_{0-t_m}^{Tot}$ for Total API,

As is demonstrated in the left plot of **Figure 1**, the AUC is for total API, including both exogenous and endogenous, if the endogenous active ingredient exists, such as epinephrine for Treatments A and B.

Figure 1 AUC for Total Active Ingredient (left) and Drug Exposure (right)

$AUC_{0-t_m}^{Tot}$ is reported in units of pg/mL*hr, can be calculated per the trapezoidal rule as given the Eq. (2):

$$AUC_{0-t_m}^{Tot} = \sum_{i=1}^{m-1} \frac{C_i + C_{i+1}}{2} (t_{i+1} - t_i) \quad (2)$$

where

- t_m is the time of the first PK point for the subject and the treatment, after C_{max} , that is reduced to the same day baseline (C_0), if C_0 is detectable, such as for epinephrine, (see **Fig. 1**, left plot); and
- $t_m > t_{max}$, and is the smallest time point that meets

$$C(t_m) \leq C_0 + \frac{1}{2} QL \quad (3)$$

- $t_m = 24$ hrs for albuterol, or m is the number of available PK measurements until t_m .

(3) The AUC for Drug Exposure $AUC_{0-t_m}^{DE}$

The AUC for the drug exposure, as is demonstrated in the right plot of **Figure 1**, is the AUC for exogenous API, if the endogenous active ingredient exist such as epinephrine for Treatments A and B.

$AUC_{0-t_m}^{DE}$ is reported in units of pg/mL*hr, and is calculated as follows:

$$AUC_{0-t_m}^{DE} = AUC_{0-t_m}^{Tot} - C_0 t_m \quad (4)$$

where $AUC_{0-t_m}^{Tot}$ and t_m is obtained based on Eqs. (2) and (3).

(4) **Drug Exposure $AUC_{0-\infty}$** (in units of pg/mL*min) is defined as below

$$\begin{cases} AUC_{0-\infty} = AUC_{0-t_m}^{DE} & \text{if } t_m < 24 \text{ hrs} \\ AUC_{0-\infty} = AUC_{0-t_m}^{DE} + AUC_{t_m-\infty}^{DE} & \text{if } t_m = 24 \text{ hrs} \end{cases} \quad (5)$$

$AUC_{t_m-\infty}$ can be obtained per the extrapolation method as given in the Eqs. (6) –(7) below, based on the time is long enough so that

$$C(t) \approx Be^{-k_e t}, \quad (6)$$

thus

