$$AUC_{t-\infty} = \int_{t_n}^{\infty} C(t)dt \approx -\frac{1}{K_e} Be^{-k_e t} \Big|_{t_n}^{\infty} = \frac{C_n}{K_e} \quad (7)$$

where $C_n = C(t_m)$ is the last available PK measurement for plasma Epinephrine or albuterol concentration, with data results greater than the analytical method's quantitation limit (QL);

K_e is the rate constant of elimination; and

B is a constant, irrelevant to time.

(5) The Elimination Rate Constant, K_e

The elimination rate constant, K_e , will be obtained using WinNonlin software.

If K_e cannot be obtained per WinNonlin (occasionally the software may not allow convergence to be achieved), or the obtained $AUC_{t-\infty}$ is 30% larger than AUC_{0-t} , then K_e for $C_1=0$ (Treatment C), will be calculated based on the least squares model from the logarithm of the last three (3) or more ($m=3, 4, 5, 6$) available PK measurements of the treatment for the subject, per the following linear equation:

$$\ln [C(t)] = a - K_e t \quad (8)$$

where $-K_e$ is the slope, and a is the intercept irrelevant to time. Then, $AUC_{t-\infty}$ will be calculated with Eq. (5).

If the baseline is greater than QL (Treatments A and B), Eq. (8) will be modified to

$$\ln [C(t) - C(0)] = a + pt \quad (9)$$

where baseline $C_1 = C(0) > 0$, the slope $p = -K_e$ can be obtained from last m data points of the given subject that are greater than the quantitative limit of the test method with least square method; where $m=3, 4, 5$ or 6 , and the obtained slope is denoted as p_m .

A consistent p_m can be accepted as the final p , for which the coefficient of variance (CV) of p_m and p_{m+1} is not more than 20%.

When m is up to 6 and $CV \leq 20\%$ is not achieved, the p_m with lowest CV with p_{m+1} will be used as the final p .

Here, m is the number of plasma samples used to calculate K_e , where $K_e = -p$.

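### The fallback Ke rule for epinephrine (SAP Eq. 9) has no cut-off at tm, so as written it fits samples already back at baseline; Eq. (7) also omits the baseline correction, which matters only when tm = 24 h

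*SAP*

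**What the plan says.** SAP 4.1.1 (2) defines tm for epinephrine as the first sample after Cmax "that is reduced to the same day baseline"; Eq. (3) makes this C(tm) ≤ C0 + QL/2. Eq. (4) subtracts C0·tm to give the drug-exposure (DE) area. Eq. (5) adds an extrapolated tail, also labelled DE, only when tm = 24 h. Eq. (7) sets that tail to Cn/Ke, with Cn = C(tm) as measured.

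SAP 4.1.1 (5) takes Ke from WinNonlin. The fallback applies if no Ke is obtained, which the SAP expects occasionally, or if the extrapolated AUC is too large relative to AUC0-t. The log-linear Eq. (8) becomes ln[C(t) - C(0)] = a + pt under this condition: "If the baseline is greater than QL (Treatments A and B". The slope comes from the last m = 3, 4, 5 or 6 "data points of the given subject that are greater than the quantitative limit of the test method with least square method". Here m "is the number of plasma samples used to calculate" Ke, so it is not the m of Eq. (2), which counts measurements until tm. A slope is accepted when p_m and p_(m+1) agree to a CV of 20% or less. Failing that, the slope with the lowest CV "will be used as the final p".

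SAP 4.1.2 derives t1/2, a secondary endpoint, as ln(2)/Ke.

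**The concern.** A terminal slope should come from samples in which the administered drug is still declining. The QL filter cannot ensure that for an endogenous substance. Eq. (9) is reserved for profiles whose baseline exceeds QL, so a sample that has returned to baseline will usually exceed QL too. Such a sample carries no information on elimination, because C(t) - C(0) is then only fluctuation around zero. Its logarithm does not exist whenever C(t) ≤ C(0), and the SAP gives no rule for that case. It also has no check on the sign of the slope and no not-estimable outcome.

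The rule is there to rescue profiles that the software cannot handle. As written, it can return nothing, a negative half-life, or a half-life of many hours for a drug that the protocol describes as short-lived. With 24 evaluable subjects, a few such values would distort a reported mean t1/2.

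Eq. (7) has a related slip. It extrapolates the measured concentration, endogenous part included, into a quantity that the rest of the section defines as baseline-corrected.

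**Working it through.** The plan states no figure on this point, so there is none to reproduce.

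**Which samples are fitted.** On the schedule in SAP 3.2.1 (Table 3), the last three samples are at 12, 18 and 24 h, and the last six at 4, 6, 8, 12, 18 and 24 h.

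**Are they back at baseline?** For inhalation, Protocol 1.4 reports: "The plasma epinephrine fell to baseline at 20 min after 30 inhalations of epinephrine". Those 30 inhalations were 4.8 mg. Treatment A is "2 inhalations, 0.25mg", and 4.8/0.25 = 19.2. The earliest of the last six samples is at 240 min, and 240/20 = 12 times later than that return. For Treatment B the documents give no half-life. An assumed 45 min leaves 2^(-240/45) = 2.5% of peak at 4 h and 2^(-720/45) = 0.0015% at 12 h.

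**Baseline level.** Protocol 1.4 says "the mean base-line epinephrine levels rose from 0.23" nmol/L and equates 1.50 nmol/L with 275 pg/mL. So C0 = 0.23 × 275/1.50 = 42 pg/mL.

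**Undefined points not skipped.** If the late samples and C(0) vary around the same level (exchangeable), at least one of the last m is at or below C(0) with probability m/(m + 1):

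- m = 3: 3/4 = 75%
- m = 4: 4/5 = 80%
- m = 6: 6/7 = 86%

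The first CV comparison needs both p_3 and p_4, so 80% of profiles get no final p. Slopes are about equally likely to have either sign in the remaining 20%, giving about 10% wrong-sign and 10% negative. Simulation with CV 10-50% agreed, with a median t1/2 of about 12-15 h in the last group. The SAP does not define p_7, so only the pairs (3,4), (4,5) and (5,6) were compared.

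**Undefined points skipped.** Assumptions: C0 = 42 pg/mL, median peak increment 150 (A) or 250 (B) pg/mL, true t1/2 20 or 45 min, QL 5 or 20 pg/mL, endogenous CV 10-30%, no drift. Every profile then gets a final p. About 15-38% have the wrong sign, and the rest have a median t1/2 of about 4-8 h.

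**Same assumptions, fit confined to samples after tmax and before tm.** Median t1/2 is about 22-26 min (true 20) and 49-59 min (true 45).

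**Eq. (7).** The baseline part of the tail is C0/Ke = C0·t1/2/ln 2:

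- t1/2 = 20 min: 42 × (20/60)/0.693 = 20 pg·h/mL
- t1/2 = 45 min: 42 × (45/60)/0.693 = 45 pg·h/mL

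When tm = 24 h, Eq. (3) limits the excess over baseline to QL/2. The largest raw tail therefore exceeds the largest corrected tail by a factor (C0 + QL/2)/(QL/2):

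- QL 5: 44.5/2.5 = 17.8
- QL 10: 47/5 = 9.4
- QL 20: 52/10 = 5.2

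Such profiles were rare under assumed inputs: tm = 24 h in 0.05-1.4% of A and 0.4-5.2% of B.

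**The case against.** **The authors may have meant something else.** SAP 4.1.1 calls Cn = C(tm) the last available measurement, so the last m points might be meant to end at tm. The QL condition might be meant for C(t) - C(0). Under assumed inputs the first reading works well, with medians of 23-28 min for a true 20 and 48-62 min for a true 45. The second is near the truth at QL 20 with CV 10-20% (21-31 and 45-52 min) but poor at QL 5. Neither is written, and the text followed literally gives the wrong fit. One clause would settle it.

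**The reach is narrow.** This stands. WinNonlin is the main method, the fallback frequency is unknown, and t1/2 is secondary and summarised descriptively. A reader might infer that AUC0-∞ and relative bioavailability are generally compromised. They are not: Eq. (5) adds no tail when tm < 24 h. The DE label on the tail also suggests that correction was intended.

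**The 80% figure depends on a convention.** This stands too. A reader might infer that the rule must fail in four of five fallback profiles. That holds only if undefined logarithms are not skipped, and the SAP does not say. Results remain poor under either convention.

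**The supporting evidence is indirect.** The 20 min return comes from six volunteers inhaling and says nothing about intramuscular dosing. The 25-50 min (A) and 80 min to 4 h (B) samples in SAP 5.1.1 items (8) and (9) are evaluability criteria, not fitting windows. They suggest where the authors expected the later phase, no more. Neither source is needed for the main point, which follows from the wording of Eq. (9).

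**Conclusion.** The concern holds in limited form. As written, the epinephrine fallback has no bound at tm and normally fits samples that have returned to baseline. For the affected profiles the resulting Ke and t1/2 are missing, of the wrong sign, or hours long when the assumed truth is 20-45 min. That qualitative result did not depend on how undefined points were handled. The percentages do, and they also rest on assumed QL, variability, peak and half-life, with no late drift in endogenous levels.

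The documents do not say how many profiles will use the fallback, so nothing can be inferred about the share of all half-lives affected. They also show no fault in the WinNonlin fit itself.

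The missing correction in Eq. (7) is a separate error. It reaches AUC0-∞, a primary endpoint, and relative bioavailability, but only when tm = 24 h, in about 0-5% of profiles under assumed inputs.

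Severity is minor to should-fix.

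**What to change.** 1. For Treatments A and B, limit the Eq. (9) fit to the last three to six samples after tmax and before tm. By Eq. (3) these all exceed C0 + QL/2, so every logarithm is defined and no further threshold is needed.
2. Report Ke and t1/2 as not estimable if fewer than three such samples remain, the slope is not negative, or tm is not reached.
3. In Eq. (7), use (Cn - C0)/Ke for epinephrine, set to zero if Cn ≤ C0.

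This is SAP wording only, with no new data.

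The cost is that some half-lives become not estimable: 2-21% of simulated profiles without drift, and 4-73% if late levels are assumed to drift to 1.5 times baseline. The Treatment B half-life may stay biased upward. For an assumed true 45 min, the bounded fit gave medians of about 49-59 min without drift and 124-143 min with it.

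What AUC0-∞ should be when tm is never reached, or when tm = 24 h and Ke is not estimable, is a separate gap in Eq. (5) for the authors to settle. This change does not resolve it.

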4.1.2 Secondary Endpoints

- (1) t_{max} is an observed value, and is represented in units of “min”,
- (2) $t_{1/2}$, terminal elimination half-life of each analyte will be reported in this study. The half-life of elimination can be calculated using K_e :

$$t_{1/2} = \frac{\ln(2)}{K_e} \quad (10)$$

4.1.3 Other PK Parameters

The elimination rate constant, K_e , and half-life of elimination, epinephrine or albuterol will be reported in this study.

4.2 SAFETY-RELATED STATISTICAL QUANTITIES

The safety evaluations will be performed based on the safety data captured directly from the electronic CRF (eCRF) or Lab report.

5. STATISTICAL DESIGN AND ANALYSIS

5.1 STUDY POPULATION

5.1.1 Per Protocol Population (PPP)

The “Per Protocol” population is defined as all subjects who have received all study medications during the study and are evaluable for all treatments. The primary analyses will be performed based on “Per Protocol” population (PPP).

An evaluable subject for primary analyses of this study must meet all of the following ten (10) items for both treatments:

- (1) Correct dose and administration;
- (2) Nineteen (19) or more of 25 post-dose PK data points (>75%) are available;
- (3) There are no more than four (4) consecutive missing PK data points;
- (4) The baseline PK data point is available;
- (5) For Treatment-A, at least four (4) of the five (5) PK data points at 1, 2, 3, 5, and 7 minutes post-dose are available;
- (6) For Treatment-B, at least four (4) of the five (5) PK data points at 9, 12, 15, 18, and 21 minutes post-dose are available;
- (7) For Treatment-C, at least four (4) of the five (5) PK data points at 25, 30, 40, 50, and 60 minutes post-dose are available;
- (8) For Treatment-A, at least three (3) of the PK data points at 25, 30, 40, and 50 minutes post-dose are available.
- (9) For Treatment-B, at least three (3) of the PK data points at 80, 90, 120 minutes and 4 hours post-dose are available; and
- (10) For Treatment-C, at least three (3) of the PK data points at 6, 8, 12 and 18 hours post-dose are available.

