6.1.1. Per-Protocol Population (PPP)

The “Per Protocol” population is defined as all subjects who have received all study medications during the study and are evaluable for all treatments. The primary analyses will be performed based on “Per Protocol” population (PPP).

An evaluable subject for primary analyses of this study must meet all of the following ten (10) items for both treatments:

- (1) Correct dose and administration;
- (2) Nineteen (19) or more of 25 post-dose PK data points (>75%) are available;
- (3) There are no more than four (4) consecutive missing PK data points;
- (4) The baseline PK data point is available;
- (5) For Treatment-A, at least four (4) of the five (5) PK data points at 1, 2, 3, 5, and 7 minutes post-dose are available;
- (6) For Treatment-B, at least four (4) of the five (5) PK data points at 9, 12, 15, 18, and 21 minutes post-dose are available;
- (7) For Treatment-C, at least four (4) of the five (5) PK data points at 25, 30, 40, 50, and 60 minutes post-dose are available;
- (8) For Treatment-A, at least three (3) of the PK data points at 25, 30, 40, and 50 minutes post-dose are available.
- (9) For Treatment-B, at least three (3) of the PK data points at 80, 90, 120 minutes and 4 hours post-dose are available; and
- (10) For Treatment-C, at least three (3) of the PK data points at 6, 8, 12 and 18 hours post-dose are available.

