5.2.2 Missing Data Handling for Non-Evaluable Subjects

Non-Evaluable Subjects will be excluded from PK evaluation.

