5.3.2.3 Relative Bioavailability (RBA)

The relative bioavailability of Treatment-A (E004 Inhalation) over Treatment-B (IM) can be defined as follows:

$$RBA = \frac{AUC_{0-\infty}^A}{AUC_{0-\infty}^B} \quad (11)$$

RBA data for each subject of are to be calculated and tabulated. The mean RBA of Treatment-A over Treatment-B of all subjects will be calculated and summarized for comparison.

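### Requiring evaluability for all three treatments lets a failed albuterol visit remove usable epinephrine A/B data from the primary results; minor and cheap to correct, with conflicting text on relative bioavailability

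*SAP*

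**What the plan says.** SAP 5.1.1 and protocol 6.1.1 give the same definition. The per-protocol set holds subjects who "received all study medications during the study and are evaluable for all treatments", and the primary analyses are run on it. The lead-in to the criteria says that an evaluable subject "must meet all of the following ten (10) items for both treatments", although the trial has three treatments.

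Items (1) to (4) are general: correct dosing, enough samples overall, no long run of missing samples, and a baseline sample. Items (5), (6), (8) and (9) concern Treatments A and B. Items (7) and (10) concern Treatment C only. Item (7) begins "For Treatment-C, at least four (4) of the five (5) PK data points" and covers 25 to 60 minutes. Item (10) reads "For Treatment-C, at least three (3) of the PK data points at 6, 8, 12 and 18 hours post-dose are available".

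Three further SAP sections bear on the consequence:

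- SAP 5.2.2: "Non-Evaluable Subjects will be excluded from PK evaluation". It makes no exception by treatment or by pair.
- SAP 5.1.2: PK parameters are also analysed in the treated population, in a supporting role.
- SAP 5.3.2.3: "The mean RBA of Treatment-A over Treatment-B of all subjects will be calculated and summarized for comparison". No analysis population is named.

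The synopsis (section V) lists RBA under additional evaluations, not as a primary endpoint. The protocol (synopsis II, 4.2.1, 4.2.2) and SAP 3.1 set the target at about 24 evaluable subjects.

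**The concern.** Treatments A and B deliver epinephrine, and Treatment C delivers albuterol. The A/B epinephrine comparison and the RBA need only visits A and B, and late albuterol samples say nothing about epinephrine exposure. No stated analysis needs all three visits from the same subject. Yet the primary set makes A and B data depend on how visit C went.

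The main stake is efficiency: valid within-subject pairs already collected go unused in the primary results. A second stake is reproducibility. The sections listed above can be read in more than one way, so two analysts could build different RBA datasets from the same SAP.

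**Working it through.** **1. Does the text produce the exclusion?**

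- *Primary epinephrine endpoints.* SAP 5.1.1 requires evaluability for every treatment and assigns the primary analyses to that set. A subject who fails item (7), item (10), or any of items (1) to (4) at visit C is outside it. The A and B profiles go with the subject.
- *RBA.* The per-protocol rule is tied to the primary analyses, and RBA is not one of them. Exclusion from RBA follows only through SAP 5.2.2, because RBA sits under PK Analysis (SAP 5.3.2). SAP 5.3.2.3 refers to every subject, which points the other way.
- *Supportive analysis.* SAP 5.1.2 keeps treated subjects in a PK analysis from which SAP 5.2.2 would remove the non-evaluable ones. Both cannot apply as written.
- *Scope of the ten items.* The lead-in speaks of two treatments and the definition of all of them. If the two were A and B, items (7) and (10) would have no role.

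**2. The plan's own figures.** Item (2) checks: 19/25 = 76%, above the stated 75%. The target of 24 cannot be reproduced, because the documents give no error rate, power, variability or dropout.

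**3. How visit C can fail alone.** Two missing samples among the five from 25 to 60 minutes fail item (7). Two missing among the four from 6 to 18 hours fail item (10). SAP 5.5.3 can also turn a late or early sample into a missing one, and its Table 4 gives no flag allowance at 40, 50 and 60 minutes.

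**4. Size.** The documents give no failure rate, so p is an assumption: the probability that a subject with usable A and B visits is not evaluable at C, independent of A and B.

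- A/B-evaluable subjects for every 24 evaluable on all three = 24/(1 − p)
- Pairs unused = 24/(1 − p) − 24
- Standard error with 24 pairs relative to the larger set = 1/√(1 − p), assuming equal variability

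| p (assumed) | A/B-evaluable | Pairs unused | SE ratio |
|---|---|---|---|
| 2% | 24.5 | 0.5 | 1.010 |
| 5% | 25.3 | 1.3 | 1.026 |
| 10% | 26.7 | 2.7 | 1.054 |
| 15% | 28.2 | 4.2 | 1.085 |
| 20% | 30.0 | 6.0 | 1.118 |

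Among 24 subjects with usable A and B visits, the chance of at least one failure at C is 1 − (1 − p)^24: 71% at 5% and 92% at 10%. The rule is therefore likely to matter for someone, but for few.

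**5. Withdrawal.** SAP 3.1 describes six sequences. A subject who leaves before visit C has both A and B only if C comes last, which is so in two of them (A-B-C and B-A-C). In the other four, A or B is lost as well and no usable pair is discarded. The table therefore fits sampling failures at C. To the extent that p reflects withdrawal, the loss is smaller.

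**The case against.** The best defence is that a common completer set is deliberate. SAP sections 1 and 2 set the three treatments side by side in the same crossover subjects, and a single set gives every column of a table the same people. That is a reasonable descriptive preference. It is weak as a reason to restrict the primary epinephrine results, because Treatment C measures a different analyte and the SAP defines no ratio that involves it. The common set can still be reported as a sensitivity analysis.

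Other parts of the defence stand and limit the point. A reader might infer the following, and the documents do not support it:

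- *That the A and B profiles are discarded altogether.* SAP 5.1.2 would keep them in a supportive PK analysis. What is clear is their loss from the primary results; the rest depends on resolving the conflict with SAP 5.2.2.
- *That the RBA certainly loses these subjects.* That follows from SAP 5.2.2 but not from SAP 5.3.2.3.
- *That the trial ends with well under 24 pairs.* If exactly 24 were treated and every visit failed independently, 24 × 0.95³ = 20.6 pairs would remain against 24 × 0.95² = 21.7 at 5%, and 17.5 against 19.4 at 10%. But the plan enrols towards 24 evaluable subjects, so about 24 pairs are expected under the current rule.
- *That power is lost.* The SAP plans listings and summary statistics; it states no A/B test, confidence interval or power.

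**Conclusion.** The point holds as a minor one. The loss of valid A and B profiles from the primary epinephrine results follows from the text. For RBA and the supportive analysis the sections conflict, so the text needs repair however few subjects are affected.

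At an assumed 5% to 10% failure rate at visit C, the cost is about 1.3 to 2.7 additional A/B pairs and a standard error about 2.6% to 5.4% larger than with them. These figures rest on the assumed rates, on independence from visits A and B, and on enrolment reaching 24 fully evaluable subjects.

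A reader might also infer that the A/B estimate is biased. That would require failure at visit C to be related to epinephrine exposure, for instance through withdrawal after a reaction at an earlier visit. It is possible, but nothing in the documents shows it, and the withdrawal route operates only when C is the last period.

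**What to change.** Define evaluability by analysis in SAP 5.1.1 and protocol 6.1.1:

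- *Epinephrine A/B endpoints and RBA:* items (1) to (4) at visits A and B, plus items (5), (6), (8) and (9).
- *Albuterol endpoints:* items (1) to (4) at visit C, plus items (7) and (10).
- *Lead-in to the items:* replace the reference to two treatments with one to the treatments being analysed.
- *SAP 5.2.2:* restate the exclusion so that it applies by analysis, and reconcile it with the treated-population PK analysis in SAP 5.1.2.
- *SAP 5.3.2.3:* name the population for the mean RBA.
- *Target of 24:* keep it tied to evaluability on all three treatments, and report that set as a sensitivity analysis.

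The cost is wording in the SAP and protocol, with no new data collection. The one downside is that subject numbers may differ between the epinephrine and albuterol tables, so each table should show its own number.

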2.1 PRIMARY ENDPOINTS

- AUC_{0-t} , defined as area under the curve (AUC) concentration curve over time, from time 0 to the time when Epinephrine reduced to the baseline post-dose for exogenous Epinephrine;
- AUC_{0-24h} , defined AUC of plasma Albuterol concentration curve over time 0 to 24 hours post-dose;
- $AUC_{0-\infty}$, defined as AUC in the plot of plasma Albuterol, or exogenous Epinephrine versus time from time 0 to infinity; and
- C_{max} , defined as the maximum plasma concentration of Albuterol, or Epinephrine.

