5.2.1 Missing Data Handling for Evaluable Subjects

For an evaluable subject that was defined in Section 5.1.1, only a small portion of PK measurements, if any, are allowed to be missed, and the interpolation method will be used for imputation.

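### A subject who lacks the 24 h albuterol sample stays evaluable, but the value reported as primary AUC0-24h then stops at 18 h or 12 h

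*SAP*

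**What the plan says.** SAP 2.1 lists albuterol AUC0-24h as a primary endpoint, "defined AUC of plasma Albuterol concentration curve over time 0 to 24 hours post-dose". Protocol 2.2 does the same.

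SAP 5.1.1 (repeated in Protocol 6.1.1) sets the evaluability items. Those that bear on late albuterol samples are:
- item (2): "Nineteen (19) or more of 25 post-dose PK data points (>75%) are available";
- item (3): "There are no more than four (4) consecutive missing PK data points";
- item (10): "For Treatment-C, at least three (3) of the PK data points at 6, 8, 12 and 18 hours post-dose are available".

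Item (7), the other Treatment-C item, covers 25 to 60 minutes. The 24 h sample is named in none of them.

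For gaps in an evaluable subject's profile, SAP 5.2.1 says that "the interpolation method will be used for imputation". No other rule is given.

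SAP 4.1.1 computes the AUC with the linear trapezoid, Eq. (2). For albuterol it sets t_m to 24 "hrs for albuterol, or m is the number of available PK measurements until" t_m. Eq. (5) adds an extrapolated tail to AUC0-∞ when t_m equals 24 h and adds none when t_m is shorter. Eq. (7) gives the tail as C_n/K_e. There C_n is written as C(t_m), and the same sentence says that it "is the last available PK measurement for plasma Epinephrine or albuterol concentration" above the quantitation limit.

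**The concern.** Interpolation needs a measured point on each side, and nothing is sampled after 24 h. If that sample is lost, the written rules leave the trapezoid sum to end at the last available time while the result keeps the AUC0-24h label. Profiles cut at 18 h or 12 h would then be averaged with complete ones in the primary population.

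The error always goes downward, so it understates exposure to the albuterol comparator. It also adds artificial spread to the between-subject variance that the protocol intends to estimate.

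A sample can drop out without being physically lost. SAP 5.5.3 treats a draw beyond its window plus flag allowance as missing. For 24 h, Table 4 gives a window of ±20 min and a proposed allowance of 40 min, so a draw more than 60 min off schedule is discarded.

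**Working it through.** **The plan's own figure.** Item (2): 19/25 = 76%, and 18/25 = 72%. So 19 is the smallest count above 75%, as stated.

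**Is the subject still evaluable?** Items (2), (3) and (10) applied to the 25 post-dose samples, all early samples present:

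| Missing | Points available | Longest gap | Item (10): of 6, 8, 12, 18 h | Evaluable |
|---|---|---|---|---|
| 24 h | 24 | 1 | 4 of 4 | yes |
| 18 h and 24 h | 23 | 2 | 3 of 4 | yes |
| 12 h, 18 h and 24 h | 22 | 3 | 2 of 4 | no |

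With 24 h missing, the profile of an evaluable subject can therefore end at 18 h or at 12 h, but no earlier.

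**Effect on AUC0-24h.** Inputs: half-life h of about 6 h (Protocol 1.4); a range of 4 to 8 h is assumed. For a mono-exponential curve, AUC0-t is proportional to 1 − 2^(−t/h). At h = 6:
- AUC0-12: 1 − 2^(−2) = 0.75
- AUC0-18: 1 − 2^(−3) = 0.875
- AUC0-24: 1 − 2^(−4) = 0.9375
- ends at 18 h: 1 − 0.875/0.9375 = 6.7% low
- ends at 12 h: 1 − 0.75/0.9375 = 20.0% low

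The linear trapezoid on the planned sampling times gives 6.8% and 20.5% at h = 6. Over half-lives of 4 to 8 h, with either no absorption phase or one that peaks at 25 or 60 min (assumed), the ranges are 3.1% to 10.1% and 11.9% to 27.2%.

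**Effect on the group mean.** With 24 evaluable subjects and similar AUCs, each affected subject lowers the mean by 6.7%/24 = 0.28% (24 h missing) or 20.5%/24 = 0.85% (both missing). Four subjects missing 24 h would lower it by 4 × 0.28% = 1.1%.

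**Effect on AUC0-∞: two readings of the same text.**
- *t_m stays at 24 h, as SAP 4.1.1 sets it for albuterol, and C_n is the last available value.* Eq. (5) adds the tail. With K_e fitted to the last three points, the result is 0.2% to 0.3% below the full-data value from 18 h, and at most 1.0% below from 12 h.
- *t_m is taken as the last sampled time.* Eq. (5) adds no tail. At h = 6 the loss is 12.6% from 18 h (closed form 2^(−3) = 12.5%) and 25.4% from 12 h (closed form 2^(−2) = 25%).

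Written as C(t_m) with t_m at 24 h, C_n does not exist when the 24 h sample is missing. That is the conflict to resolve.

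**Does extrapolation repair AUC0-24h?** The term (C_last/K_e)(1 − exp[−K_e(24 − t_last)]) was added with K_e from the last three points. It brings AUC0-24h to within about 0.3% of the full-data trapezoid from 18 h, and within about 1% from 12 h, for half-lives of 4 to 8 h. Item (10) ensures that at least three samples from 6 h onward exist for the fit, provided that they are above the quantitation limit.

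**The case against.** The strongest reply is that little depends on this. The SAP sets no hypothesis test, margin or success criterion for albuterol; it lists values and means. The one between-treatment ratio it defines, relative bioavailability, uses Treatments A and B only. The shift in the mean is well under 1% per affected subject. The 24 h draw coincides with scheduled vital signs, ECG and potassium/glucose at every dosing visit, and its timing allowance is generous. The documents give no reason to expect frequent loss. All of this stands, and it limits the weight of the point. It does not supply the missing rule.

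A reader might infer that AUC0-∞ is cut off as well. The text does not support that. For albuterol t_m is fixed at 24 h, so Eq. (5) selects the branch with a tail, and the tail is described as starting from the last available measurement. Protocol 6.2.1 also calls for extrapolation. What remains is the notation conflict in Eq. (7).

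A reader might also infer that the truncation would go unseen. SAP 5.2 requires a table of all missing samples with explanations, and individual curves and results are reported. It is fair to say only that nothing requires the affected AUC itself to be flagged, relabelled or corrected.

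Finally, requiring a later sample under item (10) looks like a natural remedy, but its cost is out of proportion. SAP 5.1.1 requires evaluability for all treatments, and SAP 5.2.2 excludes non-evaluable subjects from PK evaluation. Such a change would discard the subject's epinephrine data too.

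**Conclusion.** The point holds for AUC0-24h. Followed as written, the SAP reports an area to 18 h or 12 h under a 24 h primary-endpoint label. The shortfall is about 7% or 20% in the affected subject at a 6 h half-life (3% to 10% and 12% to 27% for assumed half-lives of 4 to 8 h). The group effect is small, about 0.3% or 0.85% of a 24-subject mean per affected subject. How many subjects would be affected is not in the documents.

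For AUC0-∞ the finding is an internal inconsistency. The more natural reading gives a nearly complete value; the other differs from it by about 12% or 25% in the same subject. The choice should be fixed before analysis.

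The sizes assume log-linear decline from the last sample and a K_e that is well estimated. This is worth correcting because the rule is biased in one direction and the correction is nearly free; it does not threaten the trial's main comparison.

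**What to change.** Add to SAP 4.1.1, with t_last the time of the last available albuterol measurement above the quantitation limit and C_last its value. If the 24 h albuterol value is missing:
- AUC0-24h = AUC0-tlast + (C_last/K_e) × (1 − exp[−K_e × (24 − t_last)])
- AUC0-∞ = AUC0-tlast + C_last/K_e

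Define C_n in Eq. (7) as C(t_last) in place of C(t_m), so that Eqs. (5) and (7) agree when the 24 h sample is absent. Flag every AUC obtained this way in the subject listings, with t_last shown. Leave evaluability item (10) unchanged.

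The cost is a few sentences in the SAP, with no change to sampling, sample size or populations. The downside is that the affected AUC0-24h values rest partly on extrapolation with an estimated K_e, which the flag makes visible.
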